#### 6) Improvement of CIVIQ-14 [Time Frame: 6, 12 weeks]

- The Chronic Venous Insufficiency Quality of Life Questionnaire (CIVIQ-14) is a valuable tool designed to evaluate the impact of chronic venous insufficiency on quality of life. Improvement in the CIVIQ-14 refers to the enhancement in scores, indicating better management of symptoms, greater comfort, and overall well-being of the patient over the course of treatment or intervention.

## 4. Research protocol and trial design

This study is designed as an investigator-initiated, single-center, open-label, pragmatic, randomized controlled trial. Patients with symptoms of lower extremity discomfort and leg edema and demonstrable venous reflux on lower extremity venous Doppler ultrasound ( $\geq 0.5$  seconds in superficial veins or  $\geq 1$  s in deep veins) will be screened for inclusion in the study. All patients who meet the inclusion criteria will be considered for inclusion.

[figure not shown]
Patients who are eligible for randomization will be randomized 1:1 to the therapeutic lifestyle change (TLC) only arm (control arm) or the medication (Entelon®) plus TLC arm (test arm). The patients will be treated for 12 weeks according to their assigned treatment arms. Patients will be evaluated for improvement in venous reflux in the target vessels and symptomatic improvement using lower-extremity venous Doppler ultrasonography at 6 and 12 weeks post-treatment.

#### 4.1. Randomization

Patients will be randomized to either the medication + TLC group or the TLC only group at the

time of enrollment in a 1:1 ratio. We plan to conduct block randomization. This process will be executed using a web-based randomization program that is managed by an independent organization.

#### 4.2. Blinding assignment

Patients will be openly assigned without blinding for the conduct of the research.

#### 4.3. Therapeutic lifestyle changes group

Implementing TLCs is a critical component of a comprehensive treatment plan for varicose veins. These non-invasive interventions focus on amending daily habits and behaviors that contribute to the progression of the condition and exacerbation of symptoms. A key aspect of TLCs is the optimization of postural habits. Patients are advised to avoid extended sitting or standing periods, which exert additional pressure on the venous system in the lower extremities and exacerbate venous insufficiency. During rest periods, elevating the legs closer to the heart is recommended because this simple yet effective adjustment promotes venous return and reduces the gravitational burden on the venous valves of the legs. The use of graduated compression stockings during waking hours is another therapeutic lifestyle intervention that is often prescribed for patients with varicose veins. These stockings exert the highest amount of pressure on the ankle, with the pressure gradually decreasing up the leg, thereby mimicking the

physiological pumping function of the calf muscles. This supports the veins in pushing blood back towards the heart, improving overall blood circulation and reducing leg swelling and discomfort associated with varicose veins.

Additional TLCs include maintaining optimal body weight and engaging in regular physical exercise. Being overweight or obese can increase intra-abdominal pressure, which can impose an additional burden on the leg veins. Regular physical activity, specifically exercises that engage the calf muscles, can improve muscle tone, enhance the efficiency of the calf muscle pump, and consequently, improve venous return. Walking or cycling are often recommended because of their effectiveness in promoting lower limb venous return.

#### 4.4. Medication + TLC group

Patients selected for the combined approach of pharmacotherapy and lifestyle modifications will receive Entelon® 150 mg twice daily for a duration of 12 weeks. This pharmacological intervention should be complemented by the adoption of improved lifestyle habits, including wearing compression stockings.

# 5. Study population

Patients with varicose veins of lower extremities will be enrolled.

#### 6. Eligiblity criteria, sample size calculation

#### 6.1. Eligibility criteria

#### 6.1.1. Inclusion criteria

- 1) Adult males and females aged between 19- and under 80-years-old
- 2) Patients with the following findings on venous Doppler ultrasound examination:
  - Superficial veins (such as the great and small saphenous veins) showing venous reflux of 0.5 seconds or longer
  - Deep veins (such as the femoral vein) showing venous reflux for 1 second or longer
- 3) Patients who have completed the washout period as described below by Visit 2, including the screening period:

- Analgesics, steroids, anti-inflammatory drugs, and venoactive medications (such as Entelon®, etc.): at least 4 weeks
- 4) Patients who voluntarily provide written informed consent to participate in this clinical trial

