#### 7. Research Procedures and Evaluation

#### 7.1. Visit 1 (Screening Visit, Weeks 4 to 2 at randomization)

Participants will visit the study site within 2–4 weeks before the study to receive an explanation of the study, provide informed consent to participate, and undergo the screening tests described below.

Patients with clinically significant abnormalities at this time will be excluded from the study.

- 1) Assignment of screening numbers: Screening numbers will be assigned according to the order in which written consent is received
- 2) Review of patient medical history and demographic information
- 3) Review of inclusion/exclusion criteria eligibility
- 4) Measurement of vital signs, height, and weight
- 5) Assessment of existing medications
- 6) Performance of blood tests and urinalysis
- 7) Performance of lower extremity venous Doppler ultrasound imaging: Patients with confirmed venous reflux times of 0.5 seconds in the bilateral superficial veins and 1 second or more in the deep veins

8) Assessment of symptoms: Venous Clinical Severity Score (VCSS), CIVIQ-14

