#### 7.2. Visit 2 (Randomization Visit, Day 0)

- 1) Review of inclusion/exclusion criteria
- 2) Review of medical/Surgical History
- 3) Physical examination and measurement of vital signs
- 4) Randomization (assignment of registration number)

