## 8.8. Symptom Assessment: VCSS, CIVIQ-14

Patients who meet the inclusion criteria will be assessed pre- and post-study using the Venous Clinical Severity Score (VCSS) questionnaire and the Chronic Venous Insufficiency Quality of Life Questionnaire (CIVIQ-14).

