# 14. Study schedule

	Baseline	Period			
Study Visit	V1	V2	V3	V4	
Period	Run-in/ Screening	Baseline	Interim Assessment	Closing	
Week/Day	-4~-2W	Day 0	6W(±14D)	12W(±14D)	
Written Informed Consenta	•				
Grant Screening No.	•				
Check inclusion/exclusion criteria	•	•			
Demographic Survey	•				
Drug administration history survey b	•	•			
Randomization (assignment of registration number)		•			
Lower extremity venous Doppler ultrasound examination	•		•	•	
Blood test and urinalysis	•		•	•	
Symptoms: VCSS, CIVIQ-14	•		•	•	
Medication history survey	•	•	•	•	
Adverse event investigations	•	•	•	•	

- a. No procedures in this study may be initiated prior to obtaining informed consent.
- b. Previous medications will be investigated and recorded only for medications used within 1 month prior to obtaining informed consent.
- c. Adverse events will be investigated after the first study-related procedure (i.e., date of signature of informed consent) until the last assessment date.

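### VCSS and CIVIQ-14 are scored before randomisation only at Visit 1, when the 4-week washout may still be running; scoring both at Visit 2 would be a cheap improvement with a small gain

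*Combined protocol and SAP*

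**What the plan says.** Section 6.1.1, criterion 3, requires "Patients who have completed the washout period as described below by Visit 2, including the screening period". The drugs and duration are "Analgesics, steroids, anti-inflammatory drugs, and venoactive medications (such as Entelon®, etc.): at least 4 weeks". The design figure in section 1 labels the interval before baseline as a run-in for washout, so stopping drugs during screening is part of the plan.

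Section 7.1 has patients attend Visit 1 "within 2–4 weeks before the study to receive an explanation of the study, provide informed consent to participate", and lists among that visit's procedures "Assessment of symptoms: Venous Clinical Severity Score (VCSS), CIVIQ-14". Section 7.2 gives Visit 2 an eligibility review, a history, "Physical examination and measurement of vital signs" and randomisation, but no symptom score. Section 14 agrees: the row "Symptoms: VCSS, CIVIQ-14" is marked at V1, V3 and V4 and is blank at V2, although V2 is the column headed Baseline. Note a to that table adds: "No procedures in this study may be initiated prior to obtaining informed consent".

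Section 8.8 names no visit: "Patients who meet the inclusion criteria will be assessed pre- and post-study using the Venous Clinical Severity Score (VCSS) questionnaire". The CIVIQ-14 form printed there asks about the past four weeks. The VCSS form states no recall period.

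The study-design summary in section 1 lists change from baseline to 6 and 12 weeks in both scores among the secondary endpoints. Section 11.2 compares continuous secondary outcomes by two-sample t-test, and also plans an analysis of primary and secondary outcomes adjusted for baseline characteristics that it does not name.

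**The concern.** The plan requires a washout and then takes no symptom score between its completion and randomisation. The washout list includes analgesics and Entelon itself, both of which bear directly on leg symptoms. For a patient who comes off such a drug, the change from the Visit 1 score to week 6 or 12 combines two things: withdrawal of the old drug, and the assigned trial treatment.

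Two groups are affected. The first stops a drug at consent. The second had already stopped before Visit 1, but not for the full four weeks. A patient in the first group also does not yet satisfy criterion 3 when scored, which sits awkwardly with section 8.8.

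At stake are the precision of two secondary comparisons and the reading of descriptive within-arm changes. The direction of the disturbance is not fixed. Stopping a drug may worsen symptoms. But the VCSS pain item gives 2 points for daily pain and 3 for daily pain with medication, so, if that medication includes analgesics, stopping one could lower the score while pain is unchanged.

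**Working it through.** **Plan's own figure.** Section 11.1 and the PASS output in section 1 use a difference of 0.8 s, SD 1.8, one-sided alpha 0.025 and 80 per arm. Power = Phi(0.8/(1.8 × sqrt(2/80)) − 1.96) = Phi(2.811 − 1.960) = 80.3%, which matches the stated 0.80260. With 20% dropout, 80/0.8 = 100 per arm. These figures concern reflux time; below they serve only as a yardstick.

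**Days off drug when scored.** Inputs: washout of at least 28 days by Visit 2 (6.1.1), Visit 1 at 14 to 28 days before Visit 2 (7.1, 14), and consent and scoring on the same day (the natural reading of 7.1, but an assumption).

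- Stops at consent: days off drug at Visit 2 equal the gap between the visits. A gap of 14 or 21 days falls short of 28, so only Visit 1 at Day -28 makes the patient eligible. Days off drug when scored = 28 − 28 = 0.
- In general: guaranteed days off drug at Visit 1 = 28 − gap, and the maximum on-drug part of the CIVIQ-14 recall = gap/28.

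| Visit 1 | Guaranteed days off drug | Maximum on-drug recall |
|---|---|---|
| Day -28 | 0 | 28/28 = 100% |
| Day -21 | 7 | 21/28 = 75% |
| Day -14 | 14 | 14/28 = 50% |

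At Visit 2 every eligible patient is at least 28 days off drug, so the on-drug recall is 0/28 = 0%. The earliest Visit 3 is Day 42 − 14 = 28. Its recall runs from Day 0 to 28 and would not overlap a Visit 2 recall (Day -28 to 0).

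**Effect on power.** The documents give neither the share of washout patients nor an SD for either score, so both the share p and the shift s (in SDs of the change score) are assumed. The effect is borrowed from reflux time: 0.8/1.8 = 0.444 SD. If a share p carries a common shift s in both arms, the variance ratio is V = 1 + p(1 − p)s², and power = Phi(0.444/sqrt(2V/80) − 1.96) for the unadjusted comparison.

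| p | s = 0.25 | s = 0.5 | s = 1.0 (extreme) |
|---|---|---|---|
| 10% | V 1.006, 80.0% | V 1.023, 79.4% | V 1.090, 76.8% |
| 25% | V 1.012, 79.8% | V 1.047, 78.4% | V 1.188, 73.2% |
| 50% | V 1.016, 79.7% | V 1.063, 77.8% | V 1.250, 71.0% |

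**Effect on within-arm change.** The offset is p × s: from 0.10 × 0.25 = 0.025 SD to 0.50 × 0.5 = 0.25 SD, or 0.50 × 1.0 = 0.5 SD in the extreme case. Its expectation is the same in both arms, so it cancels in the between-arm difference.

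**The case against.** The case for leaving the schedule alone has five parts.

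1. *The plan already has an adjusted analysis.* Section 11.2 commits to one for secondary outcomes, and section 8.2 collects medication from 4 weeks before Visit 1 up to Visit 2. Adjusting for prior washout-drug use would remove the average shift. This stands in part: the power figures above are for the unadjusted test only. But the covariates are not named, so the recovery is possible and not assured.
2. *The 0-day case is an edge case.* It needs Visit 1 exactly at Day -28 and same-day scoring. Sections 8.1 and 8.2 treat Visit 1 as the start of screening, and section 8.4 lets blood and urine tests be repeated before Visit 2. This stands as a limit on the 0-day figure. Even so, Day -28 is the only compliant timing for someone who stops at consent, and no washout patient is guaranteed more than 14 days off drug at Visit 1.
3. *VCSS is less exposed.* It has no stated recall period, and its items on ulcers, pigmentation, induration and vein extent are unlikely to move over four weeks off a drug. This stands. VCSS is affected mainly through items such as pain and edema, so a large common shift for both scores is hard to defend.
4. *The consequence is small.* The endpoints are secondary, the trial calls itself exploratory, and every input to the power range is assumed. This also stands.
5. *The Doppler has the same gap.* It too is done before randomisation only at Visit 1. True; moving the two forms is a partial remedy.

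A reader might infer that the comparison of the arms is biased. The documents do not support this: the score precedes randomisation, so the withdrawal effect falls on both arms alike in expectation.

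**Conclusion.** The point holds as a low-priority improvement. The schedule contains no VCSS or CIVIQ-14 score taken after washout and before randomisation, whichever visit is called baseline. The 0-day figure assumes same-day consent and scoring and applies only at Day -28; the 7- and 14-day figures are guaranteed minimums for patients who stopped earlier, and many may have been off drug for longer.

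The cost is noise and within-arm changes that are harder to read. For the unadjusted t-test, power falls by 0.3 to 2.5 percentage points (80.3% to between 80.0% and 77.8%) under the main assumptions. Larger losses need both common washout and a 1 SD shift, for which the documents offer no evidence. The case is clearer for CIVIQ-14 than for VCSS.

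Two further inferences should be resisted. One is that the trial is underpowered on this account: it was not sized on either score. The other is that the primary result is compromised: the documents give no basis for sizing a washout effect on reflux time, and this point makes no claim about it.

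**What to change.** Record VCSS and CIVIQ-14 at Visit 2, before randomisation so that open allocation cannot colour the answers. Add both to section 7.2 and to the V2 column of section 14, and state in section 11.2 that the Visit 2 values are the analysis baseline for the two change scores.

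The cost is a 10-item score and a 14-question form at a visit that already includes a physical examination, plus one sentence in section 11.2. No extra visit or change in sample size is needed.

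There are two downsides. Visit 2 takes a little longer. And baseline symptoms would be measured 2 to 4 weeks after the baseline Doppler, which stays at Visit 1 and keeps the same washout gap; this matters because section 3.2 links symptom severity to reflux severity. Keeping the Visit 1 scores as well preserves a same-day pairing with the Doppler where both are done that day. It also leaves two pre-randomisation values, which is why section 11.2 must name one.

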#### 6.1.2. Exclusion criteria

- 1) Peripheral arterial occlusive disease in the lower limbs
- 2) Asymptomatic lower extremity varicose veins
- 3) Acute deep vein thrombosis
- 4) Frequent lower limb pain due to neuropathy
- 5) Patients who have undergone or are scheduled for varicose vein procedures/surgeries (However, patients who have undergone a procedure or surgery more than 1 year prior to the screening date are eligible to participate.)
- 6) Patients diagnosed with systemic diseases causing edema or thrombosis, such as heart failure, endocrine diseases (hypothyroidism, Cushing's syndrome, and uncontrolled diabetes), allergic reactions to medications, urticaria and angioedema, malabsorption, protein-calorie malnutrition, obstructive sleep apnea, or thrombophilia, as determined by the investigator
  - A. History of malignancy within the past 5 years, but the following cases are eligible for clinical trial participation:
  - B. Those who have a history within the past 5 years but maintain a cured state without recurrence or metastasis
  - C. Those who have completed treatment for their tumors and have been disease-free for at least 5 years from the screening date
- 7) Those who have passed at least 1 year since the screening date after complete resection of basal cell carcinoma/squamous cell carcinoma, radical resection of thyroid papillary cancer, or successful treatment of cervical intraepithelial neoplasia
- 8) Severe renal dysfunction (serum creatinine levels more than twice the normal upper limit of the institution) on the screening date
- 9) Severe liver dysfunction (ALT or AST levels more than three times the normal upper limit of the institution) on the screening date

- 10) Need to receive diuretics or contraindicated medications and therapies that may affect the results of this clinical trial during the study period (However, patients who have been taking antihypertensive medications (calcium channel blockers, beta-blockers, angiotensin-converting enzyme inhibitors, vasodilators, and vasoconstrictors) at the same dosage for at least 4 weeks (28 days) before screening and who will maintain the same dosage and administration during the study period are eligible to participate)
- 11) History of clinically significant psychiatric disorders or alcohol abuse
- 12) History of hypersensitivity reactions to the investigational drug or its ingredients
- 13) Those who have participated in or are scheduled to participate in other clinical trials (investigational drugs, medical devices, health functional foods) within 12 weeks of the screening date
- 14) Pregnant or breastfeeding women
- 15) Women of childbearing potential who plan to become pregnant during the clinical trial participation period
- 16) Individuals deemed unsuitable for participation in the clinical trial by the investigator

#### 7. Research Procedures and Evaluation

#### 7.1. Visit 1 (Screening Visit, Weeks 4 to 2 at randomization)

Participants will visit the study site within 2–4 weeks before the study to receive an explanation of the study, provide informed consent to participate, and undergo the screening tests described below.

Patients with clinically significant abnormalities at this time will be excluded from the study.

- 1) Assignment of screening numbers: Screening numbers will be assigned according to the order in which written consent is received
- 2) Review of patient medical history and demographic information
- 3) Review of inclusion/exclusion criteria eligibility
- 4) Measurement of vital signs, height, and weight
- 5) Assessment of existing medications
- 6) Performance of blood tests and urinalysis
- 7) Performance of lower extremity venous Doppler ultrasound imaging: Patients with confirmed venous reflux times of 0.5 seconds in the bilateral superficial veins and 1 second or more in the deep veins

8) Assessment of symptoms: Venous Clinical Severity Score (VCSS), CIVIQ-14

#### 7.2. Visit 2 (Randomization Visit, Day 0)

- 1) Review of inclusion/exclusion criteria
- 2) Review of medical/Surgical History
- 3) Physical examination and measurement of vital signs
- 4) Randomization (assignment of registration number)

#### 7.3. Visit 3 (Midterm Assessment Visit, 6 weeks from randomization visit)

- 1) Lower extremity venous Doppler ultrasound (required)
- 2) Assessment of symptoms: Venous Clinical Severity Score (VCSS), CIVIQ-14
- 3) Performance of blood tests, urinalysis (optional)
- 4) Concomitant medications check (antiplatelet, antithrombotic, antihyperlipidemic).
- 5) Review of lifestyle therapy frequency of stocking wear, pharmacotherapy medication adherence checks
- 6) Monitoring of adverse events

#### 7.4. Visit 4 (End Visit, 12 weeks from randomization visit)

- 1) Lower extremity venous Doppler ultrasound (required)
- 2) Assessment of symptoms: Venous Clinical Severity Score (VCSS), CIVIQ-14
- 3) Performance of blood tests, urinalysis (optional)
- 4) Concomitant medications check (antiplatelet, antithrombotic, antihyperlipidemic).
- 5) Review of lifestyle therapy frequency of stocking wear, pharmacotherapy medication adherence checks
- 6) Monitoring of adverse events

#### 8. Methods

#### 8.1. Demographic Information

At Visit 1 (Screening Start Date), we will conduct a demographic survey of the participants' initials, date of birth, sex, age, smoking, alcohol use, BMI, occupation, and standing time.

#### 8.2. Medical History and Prior/Concomitant Medications

Medical history is defined as any medical condition that has been ongoing for less than 1 year as of Visit 1 (screening start date), including past medical history (hypertension, diabetes, hyperlipidemia, previous PCI, previous myocardial infarction, peripheral vascular disease, heart failure, CVA, dialysis, CABG) and clinically significant diagnostic findings from blood chemistry, urinalysis, physical examination, endoscopy, etc. performed up to Visit 2. In addition, the history of medications within 4 weeks (28 days) of Visit 1 (screening start date) and up to Visit 2 will be investigated and collected as prior medications, and the history of medications at Visit 2 will be collected as concomitant medications.

## 8.3. Vital Signs and Physical Examination

At each visit, the sitting blood pressure (systolic and diastolic), heart rate, and body temperature will be measured. Blood pressure, heart rate, and temperature will be measured after 5 minutes of rest and, if possible, prior to all scheduled tests.

At each visit, the patients be weighed and observed for the following: Height will only be measured during screening. A physical examination will be performed by the investigator, who will examine the patient's body for clinically significant abnormal symptoms and signs, excluding medical history, by palpation, tapping, and auscultation. The physical examination that is performed after screening focuses on the presence of clinically significant changes compared to the previous examination. Physical examinations include the weight, cardiovascular system, peripheral vascular system, skin/mucous membranes, eyes (excluding vision impairment), ENT, respiratory system, musculoskeletal system (excluding hernias), infectious diseases (excluding childhood diseases), gastrointestinal tract/liver/biliary system (excluding appendectomy), endocrine system, renal/genitourinary system, neurological/psychiatric system, tumors, fractures, and surgery.

